Specific Aim 1 (Completed): In consultation with expert qualitative researchers, we have completed separate qualitative interviews of 53 Nemours adolescent patients with T1D and parents/caregivers who have previously made a decision (*pro or con*) about initiating CSII or CGM. Interviews obtained their perspectives of the decision making process, their post-decision experiences and their recommendations regarding how their decision making could have been enhanced. We have conducted similar interviews with 14 pediatric endocrinologists and certified diabetes educators from throughout Nemours.

Specific Aim 2 (Completed): With input from parents and adolescents who have previously faced one of these decisions, Nemours Center for Children’s Health Media, pediatric endocrinologists, certified diabetes educators, and three expert consultants in qualitative research and shared medical decision making (Drs. [name], [name] and [name]), we have prepared and iteratively refined for use in pediatrics multi-media “Decision Aids” on CSII and CGM for dissemination via a web platform meeting the International Patient Decision Aids Standards. After obtaining a username and password to be provided separately, IRB members, consultants and others can explore final versions of these tools at these websites:

<https://Nemours.MyPumpChoice.org/> and <https://Nemours.MyCGMChoice.org/>.

Specific Aim 3: The current study is a multi-site randomized trial of SMDM versus usual clinical practice (UCP) with 166 11-<17 year old patients with T1D who are candidates for CSII or CGM and their parents. This study will evaluate the effects of the SMDM intervention over 1 year on primary outcome measures of: quantity and quality of use of CSII or CGM if selected and measures of decision quality, CGM or Pump knowledge and satisfaction with CSII or CGM, and on secondary outcome measures of T1D treatment adherence, glycemic control and diabetes-related distress. Utilization of the decision aids will be tracked carefully. These points justify our specific aims:

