Exclusion Criteria for Youths: Concurrent participation in any other research in which treatment adherence or glycemic control are study outcomes; Daily oral glucocorticoid treatment; Significant developmental delay (self-contained special education; retention in 2 or more grades); Inability to read/comprehend study questionnaires and decision aids in English; Treatment for a coincident medical condition that, in the opinion of the treating physician, represents a contraindication to study participation.

Inclusion Criteria for Parents: Primary diabetes caregiver of index child; Anticipates continued medical care for T1D at Nemours or the Barbara Davis Center for subsequent year; capable of participating in conversations during medical visits; routinely accompanies child for diabetes care at Nemours or the Barbara Davis Center.

Exclusion Criteria for Parents: Inability to read/comprehend study questionnaires and decision aids in English; Child living in a temporary placement such as foster care or juvenile detention center; Evidence of frequent changes in the adolescent's household or living arrangements.

Recruitment, Parental Permission and Adolescent Assent: The study will be approved by a Nemours IRB before recruitment begins. All Nemours health care providers who see patients for management of type 1 diabetes, and who may be in a position to evaluate and prepare candidates for incorporation of either CSII or CGM into their care plans, will receive an initial e-mail describing the study and announcing the opening of enrollment. HCPs will be provided with a link to the web-based decision aids for their inspection. A total of 13 Nemours pediatric endocrinologists and diabetes educators provided information and feedback that has been

incorporated into the decision aids as they were being developed.

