Recruitment Plan C: This strategy will be used in those instances in which a family is recruited remotely. The study will be advertised with a brief description of the study in the Childrenwithdiabetes.com website. The description will include a link for more information that will take them to a study flyer within REDCap. Then if they express interest in participating in this research, the informed consent and assent forms will pop up. Families will be offered the opportunity to speak with a representative of the research team if they wish to do so before signing the consent and assent forms. The document will conclude with an electronic signature process consisting of either signing with their mouse or if using a touchpad, signing with their finger. They will have an opportunity to print the forms prior to submitting them (families that are consented electronically will also have a copy of the signed consent forms emailed to them). Prior to submitting the signed consent and assent forms, the family will complete a few contact information questions, so that a research coordinator may contact them to get them started in the study. There will be other minor modifications to the study procedures for families enrolled remotely: study visits will not need to directly coincide with clinic visits therefore can disregard references to clinic visits; participant's diabetes physician will not play a role in the study (other than to inform him/her of the participant's enrollment and to ask for copies of A1cs); a diabetes educator nurse will

not be completing the SMDM Intervention Summary Form.

[figure not shown]
Childrenwithdiabetes.com also has a couple of international Friends for Life conferences a year, in which we will also try to recruit participants both in person and by having flyers distributed to attendees of the conferences (Church Falls conference April 8-10, 2016 and Orlando conference July 5-10, 2016).

Randomization Procedures: Once a given adolescent/parent dyad completes all baseline measures, they will be randomly assigned with equal probability to one of the two study conditions described below.

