Data Management and Statistical Analysis Plans The primary efficacy endpoints are indices of extent of engagement in CSII (mean number of bolus infusions/day; mean number of uses of "wizard" functions/day) or CGM use (mean number of hours of CGM use/day); and measures of decision quality (Test of CSII or CGM Knowledge; SURE Test; Decision Regret Scale; Diabetes Technology Questionnaire) at each post-decision visit. Secondary efficacy endpoints will include: HbA_{1c} measured quarterly, treatment adherence (DSMP-SR parent and youth) total scores obtained at Visits 1, 3 and 5; and Hypoglycemia Diary obtained at each quarterly clinic visit.

The Full Analysis Set will consist of all participants who provided at least one post baseline assessment record. The Completer Analysis set will include all participants who provided all post baseline primary efficacy assessment results.¹⁶⁶⁻¹¹⁶⁸ Efficacy analyses will be performed on both sets, providing both "Intention to Treat" (Full Analysis Set) and "Per-Protocol" (Completer Analysis Set) analyses. All collected data will be summarized in graphs and tables. Categorical variables will be summarized using frequencies and percentages, while quantitative variables will be described by presenting mean, median, standard deviation (or standard error of mean), minimum and maximum. Data will be summarized by group (SMDM and UCP) and type of medical decision (CSII or CGM) as well as assessment time points. Besides tabular presentation, graphical presentations of some important variables related to primary and secondary endpoints will be provided.

Assumptions for all proposed models will be checked before statistical analyses.¹⁶⁶⁻¹⁶⁸ Appropriate transformations or non-parametric methods will be used in cases of violated model assumptions. For graphical comparison of data that are sufficiently normally distributed, group means and SE of mean will be presented via bar charts. In case of substantial deviation from normality, side by side boxplots will be used for graphical comparisons. Exploratory Subgroup analyses will be conducted as needed. All tests will be performed against a two-sided alternative at the $\alpha = 0.05$ significance level and a 95% confidence interval and/or a p-value will be provided for inferential purposes. Data from all clinics will be pooled for the analyses. All analyses will be performed using the most recent version of the SAS statistical software package.

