Five parents and their seven adolescents with T1D were recruited to serve as members of a Family Advisory Council. They were selected to reflect diverse representation in terms of Nemours sites, socioeconomic status, race/ethnicity, gender and prior experience related to insulin pump therapy and continuous glucose monitoring. Each FAC dyad will be paid \$500 annually to compensate them for expenses they incur due to their FAC participation. In constituting this group, we began by carefully examining the participants in [name] ongoing NIH-funded trial of continuous glucose monitoring, from which we were able to identify adolescents who did or did not experience CGM use and who did or did not demonstrate glycemic or quality of life benefits from doing so. This group of 104 research participants consists of 67% non-Hispanic Caucasians, 21% African-Americans and 12% Hispanics, with very diverse educational attainment and household income. Similarly, we will be able to identify adolescents whose insulin delivery modalities were either insulin pumps or multiple daily insulin injections during that study.

The FAC will be convened in monthly meetings using video or telephone conferencing facilities that are in place at all Nemours operating entities. Each meeting will be audio-recorded and minutes will be taken and distributed to all members. The FAC will select its own chair, who will prepare the meeting agendas and manage the discussion of the specific agenda items. The FAC will be considered advisory to the research team, in that their recommendations will be given very serious consideration, but final decisions regarding study design, implementation or interpretation will rest with [name] and the Co-Investigators. The initial charge of the FAC will consist of review of, and commentary on, the study protocol, procedure manual, and human subjects protection plan. Since an external and independent Data and Safety Monitoring Board is

unnecessary for this research since it poses minimal risk to participants, the FAC (with participation by [name], [name] and one of the endocrinologists) will provide study oversight regarding the recruitment experience, and the occurrence of any data quality issues, threats to privacy or confidentiality, other unanticipated problems, participant complaints or other such issues.

Prospective FAC members have received this list of expectations regarding their involvement :

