- Learn some basics about how research is planned, completed and analyzed
- Learn about the study plans and become very familiar with what other families will experience
- Try out the decision aids to become very familiar with them
- Complete study questionnaires and give feedback to us about instructions and wording
- Participate in video conferences or phone conferences with the research team about once per month
- Help us to develop a research informed consent form that is complete but also easy to understand
- Help us plan how we can best get families to join the study and to stay in it for a year
- Be a voice on the research team for families who are participating in the research
- Be a partner in writing papers or presenting research results at conferences

Input from T1D Health Care Providers

Parallel to the solicitation and incorporation of input from the FAC, Nemours health care providers (HCPs) who provide clinical care and education to patients with T1D and their families have served as key stakeholders whose feedback about the study design and implementation is fundamental to the conduct of this research. During the completed qualitative interview study, input from 13 Nemours HCPS was obtained about their perspectives of their current and ideal practices regarding the decision to start patients on insulin pumps or continuous glucose monitors, their recommendations regarding the structure, content and process of the planned SMDM intervention, methods to merge the SMDM intervention with their established clinical and educational routines and their specific comments on the successive iterations of the Decision Aids.

Interviewers posed a series of structured questions and the responses were audio-recorded and subsequently transcribed verbatim for descriptive qualitative analysis. Our consultants, Drs. [name], [name], [name] and [name], assisted in refining the questions to be asked, training the interviewers, providing the interviewers with open-ended follow-up questions designed to probe or expand upon the initial responses, and assisting the research team in condensing and incorporating this feedback into concrete refinements to the decision aids or intervention plans. In addition, [name], of KidsHealth, and [name], our consultant, are practicing pediatric endocrinologists and each of them provided extensive input into the planning and content of the two decision aids.

Qualitative Interview Study

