As described in detail in the Research Strategy, a Qualitative Interview Study (QIS) was completed during the first year of the planned research. This involved 53 parent-adolescent dyads who had previously made a decision, *pro or con*, regarding the initiation of either insulin pump therapy or continuous glucose monitoring as a component of their T1D care. The interviews were designed to achieve two purposes: 1.) To gain a thorough perspective of how these families made their decisions, their satisfaction with their decision making process and outcomes and their suggestions for how their decision making could have been improved; and 2.) Their perspectives on successive iterations of the Draft Decision Aids until the FAC, the research team and the Nemours Center for Children's Health Media staff are satisfied that these tools cannot be improved further. Interviewers posed a series of structured questions and the responses were audio-recorded and subsequently transcribed verbatim for descriptive qualitative analysis. Our consultants assisted in refining the questions to be asked, training the interviewers, providing the interviewers with open-ended follow-up questions designed to probe or expand upon the initial responses, and assisting the research team in condensing and incorporating this feedback into concrete refinements to the decision aids or intervention plans.

End-of-Study Qualitative Interviews

An important objective of this research is to take away lessons that may inform future research on shared medical decision making in pediatrics and that may guide the preparation of decision aids and SMDM interventions related to other preference-sensitive decisions that arise in pediatrics. Using the same questions employed in the qualitative interview study, each participant will be interviewed again upon exiting the randomized trial of SMDM regarding their experiences during that study and their suggestions for how the decision aids or intervention delivery could be improved to enhance their decision quality.

Governance Plan

The Family Advisory Council will meet monthly via conference call. Compensation is budgeted in the

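### No criterion excludes families who have already seen the decision aids, and no rule covers two eligible children of one caregiver, so aid-exposed families can be randomized to usual care

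*Combined protocol and SAP*

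**What the plan says.** **Eligibility.** The only research-related youth exclusion in B.1 is "Concurrent participation in any other research in which treatment adherence or glycemic control are study outcomes". The list in C.3 (Participants and Eligibility Criteria) restricts this to diabetes research but is likewise about concurrent studies. The parent exclusions in both places cover reading ability in English and household or custody circumstances. None mentions earlier contact with the decision aids. The General Information Form (B.3) records past pump or CGM use, not aid exposure.

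**Who has had contact with the aids.** Specific Aim 1 reports that "we have completed separate qualitative interviews of 53 Nemours adolescent patients with T1D and parents/caregivers". Part D (Qualitative Interview Study) gives as the second purpose of those interviews "Their perspectives on successive iterations of the Draft Decision Aids until the FAC, the research team" and others were satisfied with them. For the council, Part D says "Five parents and their seven adolescents with T1D were recruited to serve as members of a Family Advisory Council"; its listed expectations include "Try out the decision aids to become very familiar with them" and completing the study questionnaires. The KidsHealth task list also provides for adolescents and parents to review a beta version.

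**Randomization.** B.1 says "Once a given adolescent/parent dyad completes all baseline measures, they will be randomly assigned with equal probability to one of the two study conditions", from a separate list for each site. It states what happens when two caregivers of one child enroll. It does not state what happens when one caregiver has two eligible children.

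**Endpoint.** B.5 names the Knowledge Test among the primary efficacy endpoints. B.3 describes it as a five-item test drawn from the content of the aids.

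**The concern.** The comparison is between usual education and the same education plus the decision aids with supporting contacts. A UCP family that already knows an aid has received part of the experimental treatment, and the contrast shrinks. The Knowledge Test is the most exposed endpoint because its items come from the aids. B.3 requires that test to be taken in person so that families cannot look up the content. The plan thus already treats outside access to this material as a threat but leaves this route open. Because exposure is neither an exclusion nor a recorded baseline variable, the plan provides no data with which to identify these families at analysis.

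**Working it through.** **1. Could an exposed family qualify?** Interview dyads had already decided for or against a device, and entry requires that a pump or CGM decision be open. Recruitment Plan B takes only dyads not previously considered candidates for either device, so it should not admit them. Recruitment Plan A has no such limit: a care provider identifies the family before a scheduled visit. B2 expects decisions in sequence, such as a pump first and CGM later, and a family that declined may reconsider. An exposed family can therefore enter as the plan is written.

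**2. Could a sibling be assigned to UCP?** Assignment is by adolescent/parent dyad within site. B2 encourages SMDM families to share the aid with supportive persons. Five council parents with seven adolescents with T1D show that households with more than one affected youth exist in this clinic population. Nothing prevents opposite assignments within a household.

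**3. Inputs for the size.** Enrollment 166 at 1:1 gives 166/2 = 83 per arm (B.1, B.5). The planned effect is about 0.4 SD, with 150 completers (75 per arm) and stated power .87 (B.5, Statistical Power). B.5 adds: "All tests will be performed against a two-sided alternative at the" 0.05 level. The number u of exposed UCP families is not in the documents. I assume 2 to 8.

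**4. The plan's own figure.** Power = Φ(d√(n/2) − 1.96). With d = 0.4 and n = 75, this is Φ(2.449 − 1.960) = .688, not .87. Reaching .87 two-sided needs d of about 0.504. This mismatch is a separate matter and does not affect the present point; both bases are shown below.

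**5. Dilution.** Suppose an exposed UCP family gains the whole SMDM effect. The expected contrast is then d × (1 − u/83). For d = 0.40 and u = 2, that is 0.40 × 81/83 = 0.390.

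| u exposed of 83 UCP | Share | Effect from 0.40 SD | Power, 0.40 SD basis | Power, 0.504 SD basis |
|---|---|---|---|---|
| 0 | 0% | 0.400 | .688 | .870 |
| 2 | 2.4% | 0.390 | .667 | .854 |
| 4 | 4.8% | 0.381 | .645 | .836 |
| 8 | 9.6% | 0.361 | .600 | .796 |

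Each exposed UCP family costs 1/83, or about 1.2%, of the effect and about one point of power.

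**6. What the range implies.** Exposure before the trial should split evenly at randomization, so u in UCP needs about 2u exposed families enrolled: about 4 for u = 2 and about 16 for u = 8. The interview and council families come from Nemours. If the Denver commitment of 80 patients/parents means 80 dyads, 166 − 80 = 86 families come from elsewhere, about 43 of them in UCP. Eight would then be 8/43, or about 19%, of that group, so the upper end is already a strong assumption.

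**The case against.** The best case against acting is that few exposed families would enroll and that the bias is conservative. Interview families had already made their decision. The Project Plan puts the interview study in the first 9 months and the start of trial recruitment at about month 21, so some older interviewees will have passed 18. The council has only five parents. The websites need an issued login. Exposure before randomization is balanced in expectation. Viewing a draft, perhaps for the other device, does not supply the orientation, educator review, written summary and return visit that make up the rest of SMDM. All of this stands, and it limits the size. It does not close the gap, because none of it is an eligibility rule.

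Some stronger readings are tempting but unsupported:

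- A reader might add 53 and 7 and say that at least 60 exposed adolescents are in the source clinics. The documents do not say that the two groups are distinct, or that every interviewed dyad saw a draft; Specific Aim 1 describes the interviews without mentioning drafts.
- Carrying that sum further, 60/2 = 30 of 83 UCP families would cut 0.40 SD to about 0.26 SD. That requires every one of them to enroll, and nothing suggests this.
- A reader might infer that many of these families are now candidates. No figure supports that.
- The KidsHealth section lists a search for local families to appear on camera. It does not say that they viewed the aids.
- A reader might infer that council members would be trial subjects while sitting on the oversight group. The documents do not bar this, but they do not suggest that any would enroll; Part D describes them as working in effect as part of the research team.

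**Conclusion.** The gap is real: followed as written, the plan allows a family that has seen an aid, or a sibling of a child whose parent is using one, to be randomized to UCP. The bias is toward no difference, most directly on the Knowledge Test. Its size is unknown and probably small. With 2 to 8 exposed of about 83 UCP families, a 0.40 SD effect falls to about 0.39 to 0.36 SD, and power falls by about 2 to 9 points on the 0.40 SD basis. The counts are assumptions. For any given count the loss is an upper bound, because the calculation credits viewing alone with the full SMDM effect. Nothing here threatens a false claim of benefit. The change is worth making because it is cheap before enrollment, and unrecorded exposure cannot be dealt with at analysis.

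**What to change.** 1. **Exclusion.** Add to the youth and parent exclusions in both B.1 and C.3: any youth or parent who previously viewed a draft or final version of either decision aid. Name interview participants who were shown drafts, council members and beta reviewers. Check against the study's rosters and ask one screening question.
2. **Household rule.** Add to Randomization Procedures in B.1 that only one index adolescent per household is randomized. Alternatively, a later-enrolling sibling takes the household's existing assignment, with household clustering handled in the mixed model. If the same-assignment rule is chosen, the exclusion must exempt viewing that came from the household's own trial assignment. That sibling's arm would also be known before consent, so the one-index rule is the simpler choice.

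Do not offer a sibling the assigned condition outside the analysis sample: that would add diabetes educator time that the budget does not show.

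The cost is the loss of a few otherwise eligible families, one screening question and a roster check. If the sponsor will not give up those families, the minimum is to record prior exposure at baseline and to specify a sensitivity analysis without exposed families.

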Randomization will be implemented by [name], MACP, Senior Research Coordinator in Jacksonville, using a separate randomization list for each enrolling site, to ensure that each site enrolls an approximately equal number of participants in each of the two conditions. Two or more adult caregivers for a given child may enroll in the study, in which case study questionnaires will be completed jointly by consensus of those caregivers. Some adolescents may first become a candidate for one of the devices (CSII or CGM) and thereafter become a candidate for the other. In such instances, the adolescent will remain in the same condition throughout the remainder of the study as was dictated by the initial random assignment.

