B.3. Measures: Just as the recruitment procedures have been designed to provide flexibility to prospective participants in terms of how they would enter the study, the measurement plan has also been designed to afford flexibility to participants in terms of how, where and when they will complete the various questionnaires for this project. The only measures that must be completed in person are the CSII and CGM Knowledge Tests, the Rapid Estimate of Adult/Adolescent Literacy in Medicine and the Diabetes Numeracy Test. Other study questionnaires will be available for online completion via internet access utilizing the REDCap electronic data capture software. [name], MACP, Senior Research Coordinator, has been trained fully in developing questionnaires in this format and she has had additional expert consultation available from [name]. of the AIDHC Bio-Informatics group. All study measures are included in a separate Appendix that is attached.

Study visits will be scheduled to be coincident with regularly scheduled diabetes clinic visits, which are expected to occur at approximately quarterly intervals for most participants. The mixed models analyses that constitute the core of the analysis plan can robustly accommodate variations in data collection schedules across participants. Adolescents and parents will each receive reminders (via e-mail, phone, text message or social media according to their preference) 2 weeks prior to the next study visit reminding them of the visit and enabling them to complete any scheduled questionnaires online. Another reminder will be sent again 5 days prior to the scheduled visit to participants who have not yet completed the questionnaires. Those who do not do so online will complete questionnaires at the clinic. In rare instances, the research team may offer the possibility of conducting home visits for collection of these measures. These procedures for online questionnaire administration were used successfully in [name] recent NIH-funded trial of CGM. Total time commitment from parents and adolescents for completion of measures is ~75 min at Baseline and ~60 min at Visits 3 and 5. Visits 2 and 4 will entail little added participation burden.

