family has reached a decision about CSII or CGM). Equivalent forms of this test were developed and participants will complete one form at Visit 1 and the other form at Visit 2. At each of those visits, parents and adolescents will complete different forms of the test. These measures must be completed in person to prevent interactions between parents and adolescents and to prevent use of written or online information related to the test content.

Measures obtained at Baseline (Visit 1), Visit 3 and Visit 5

Diabetes Technology Questionnaire (DTQ): This is a 30-item questionnaire that assesses satisfaction with a patient's defined "package" of diabetes technology in use (i.e. blood glucose meter, insulin pump or CGM). Parents and youth rate their satisfaction with and perceived impact of the specific cluster of technological elements that they have been using for the prior 3 months. The DTQ is an adapted version of the CGM Satisfaction Scale developed by [name] for the DirecNet and JDRF CGM trials,^{17, 19-20, 150-151} and it is used in [name] current CGM trial. Internal consistency ($\alpha = .91$), test-retest reliability over 3 months ($r = .57$ to $.66$) and parent-youth agreement ($r = .65$) have been excellent. Parents and youth in both groups will complete this questionnaire at Visits 1, 3, and 5. There are separate versions for baseline and follow-up administration. Administration time is 10-15 minutes.

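### Remote recruitment (Plan C) is not reconciled with the plan's own eligibility, in-person testing, intervention and randomization rules

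*Combined protocol and SAP*

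**What the plan says.** Plan C (B.1) advertises on an external diabetes website, takes electronic consent, and lists changes that it describes as minor:

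- On visits: "study visits will not need to directly coincide with clinic visits therefore can disregard references to clinic visits".
- On the provider: the "participant's diabetes physician will not play a role in the study", except that the physician is told of enrolment and asked for HbA1c results.
- On the intervention: a diabetes educator nurse will "not be completing the SMDM Intervention Summary Form".

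The rest of the plan keeps these rules:

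- **Care site.** The sample in B.1 is patients receiving diabetes care at Nemours or the Barbara Davis Center. The parent criterion is "Anticipates continued medical care for T1D at Nemours or the Barbara Davis Center for subsequent year", and the parent must also routinely accompany the child there. C.3 repeats the care-site requirement.
- **Candidacy.** B.1 requires that the treating provider regard the youth as a suitable CSII or CGM candidate. The Practical considerations table in B.2 treats a youth as ineligible until the provider agrees.
- **Order of events.** Randomization Procedures: "Once a given adolescent/parent dyad completes all baseline measures, they will be randomly assigned with equal probability".
- **In-person testing.** B.3: "The only measures that must be completed in person are the CSII and CGM Knowledge Tests", together with the literacy and numeracy tests. For the Knowledge Test the reason is given: "These measures must be completed in person to prevent interactions between parents and adolescents and to prevent use of written or online information".
- **Lists.** The coordinator randomizes "using a separate randomization list for each enrolling site".
- **Intervention.** B.2 lists the educator's individual summary and a return visit to the provider among the SMDM components, and says the intervention ends with that visit.
- **Analysis.** B.5 makes the Knowledge Test a primary endpoint, pools data from all clinics, and states no site or remote term.

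**The concern.** Plan C opens a recruitment route without amending the rules that the route touches. Coordinators would have to decide, family by family, whether to waive the care-site criterion, how to establish candidacy, and under what conditions to give the tests. A reader could not then tell which rule had been applied to whom.

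Two effects on the comparison follow.

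- **Knowledge Test.** If the in-person rule is relaxed without a substitute, a primary endpoint is measured under conditions that differ by arm. At baseline, looking up answers is not arm-related, because nobody has been randomized. At the post-decision test, SMDM families have been given the website on whose content the test is based. The Measurement Schedule collects utilization statistics through Visit 5, which suggests that access stays open.
- **Other primary endpoints.** If remote SMDM has less effect because two listed components are missing, pooling it with clinic-delivered SMDM pulls the estimated effect towards zero.

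**Working it through.** **Rules set side by side**

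| Rule | Requirement | What Plan C provides |
|---|---|---|
| Care site (B.1, C.3) | Continuing care at, and accompanied visits to, a study centre | No waiver; website families would generally not qualify |
| Candidacy (B.1, B.2) | Treating provider supports it | No step to confirm it |
| Baseline before randomization (B.1) | All measures, including three in person | No in-person testing occasion described |
| Knowledge Test safeguard (B.3) | In person at both administrations | No substitute |
| SMDM components (B.2) | Educator summary and concluding provider visit | Form not completed; physician has no role |
| Randomization lists (B.1, B.2) | One per enrolling site | No remote stratum named |
| Analysis (B.5) | Clinics pooled | No remote term |

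The first row is a direct conflict. The second to fourth and the last two are omissions. The fifth is a stated change to the intervention that the analysis does not recognise.

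**The plan's power figure**

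Inputs from B.5: 166 enrolled, 10% attrition, about 150 completers (166 × 0.9 = 149.4), hence 75 per arm; effect 0.4 SD; two-sided alpha 0.05; stated power 0.87.

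For a two-sample t test the noncentrality is d × √(n/2) = 0.4 × √37.5 = 2.45 on 148 degrees of freedom, giving power 0.68. The stated 0.87 is not reproduced; it corresponds to roughly 0.5 SD (power 0.86). That is a separate matter. Here 0.68 serves only as the starting value.

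**Illustration of dilution**

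Assume a remote share f and let remote SMDM keep a fraction k of the effect. Neither is in the documents. The pooled effect is d = 0.4 × (1 − f + f × k).

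| f | d, k = 0.5 | Power | d, k = 0 | Power |
|---|---|---|---|---|
| 0.1 | 0.38 | 0.64 | 0.36 | 0.59 |
| 0.2 | 0.36 | 0.59 | 0.32 | 0.49 |
| 0.3 | 0.34 | 0.54 | 0.28 | 0.40 |

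**Illustration of Knowledge Test bias**

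Assume 20% of families are remote, half of remote SMDM families look up answers, the gain is 1 SD, and UCP families gain nothing. The contrast is inflated by 0.2 × 0.5 × 1 = 0.1 SD, a quarter of the 0.4 SD target. If UCP families also look things up, the bias is smaller.

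**Leaving remote families out of the Knowledge endpoint**

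With 10%, 20% or 30% omitted, the per-arm numbers are 67.5, 60 and 52.5. Power at 0.4 SD is then 0.64, 0.58 and 0.53.

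**The case against.** Several stronger readings are tempting, and the documents do not support them.

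- **That no remote family can ever be randomized.** Plan C keeps study visits and only uncouples them from clinic visits. It goes on to describe recruitment in person at conferences, B.3 allows home visits exceptionally, and Plan B provides a separate appointment for the in-person tests. In-person testing is therefore unprovided for under Plan C, not excluded. Even so, a conference contact would not cover the second Knowledge Test or meet the care-site criterion.
- **That candidacy must be judged by a provider taking part in the study.** B.1 asks only for the treating provider's view. A family's own physician can hold it, and Plan C has staff contacting that physician. What is missing is a step to verify it.
- **That remote SMDM is the website alone.** Plan C drops the educator's form, not expressly the educator's consultation. B.2 allows orientation by telephone, and the SMDM version of the decision-making form in the appendices refers to video sessions with an educator. The loss shown is the written summary and the concluding provider visit.
- **That the missing list prevents randomization or biases it.** The plan is silent here. The coordinator could create a list, and allocation would remain 1:1.

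In addition, a figure following Plan C is not reproduced, and the visit checklists are held outside the document, so some detail may exist there. This tempers any claim of complete absence. It does not remove the conflict between the stated care-site criterion and website recruitment, or the lack of a substitute for the Knowledge Test safeguard in the protocol text.

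**Conclusion.** The point holds as a failure to reconcile. Plan C leaves in force a care-site criterion that its website recruits would generally not meet. It gives no way to confirm candidacy, does not provide for the three in-person tests or replace the Knowledge Test safeguard, changes the delivered intervention without an analysis term, and names no remote stratum.

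The likely direction is inflation of the Knowledge contrast if that test is taken unobserved, and dilution of the other contrasts if the lost components matter. The size cannot be established. The power range of 0.64 to 0.40 (from a recomputed 0.68) and the 0.1 SD inflation rest on assumed values for remote share, relative effect, look-up rate and look-up gain. The inconsistencies in the text do not depend on those values. The matter should be corrected before remote families are enrolled.

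**What to change.** 1. Reconcile the care-site and candidacy criteria in B.1 and C.3 with Plan C, and state how candidacy is confirmed and recorded for a remote family.
2. Give the Knowledge, literacy and numeracy tests to remote parents and adolescents separately, on a live observed video call, at each occasion when they are due. Failing that, waive them as a precondition for randomization in remote families and leave those families out of the Knowledge endpoint, accepting the loss of power shown above.
3. State which of the SMDM components listed in B.2 remote families receive.
4. Make remote enrolment its own randomization stratum, and include the strata in the models.
5. Keep all randomized families in the primary analysis. Report an arm-by-remote term and a sensitivity analysis restricted to clinic-enrolled families.

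The cost is amendment wording with IRB review, one more randomization list, and about 15-20 minutes of coordinator time per test occasion, which is the time Plan A allows for these tests. The arm-by-remote term will be imprecise if few families enrol remotely, so it should be read as descriptive.
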